7.5 MTD Determination

This MTD determination applies to the Safety Portion. MTD for the safety portion will be defined as the dose level below the lowest dose that induces dose-limiting toxicity in at least one-third of subjects (at least 2 of a maximum of 6 subjects).

- 7.51 Three subjects will be treated at a given dose level combination and observed for one cycle to assess toxicity (accrual will be suspended while the 3 subjects are treated and observed – only applicable to the dose escalation cohort/ part of study).
 - 7.52 If DLT is not seen in any of the 3 subjects or in 1 of 3 subjects, 3 new subjects will be accrued and treated at the same dose level (accrual will be suspended while the 3 subjects are treated and observed). If DLT is seen in 2 or 3 of 3 subjects treated at a given dose level, then the next 3 subjects will be treated at the next lower dose level, if only 3 subjects were enrolled and treated at this lower dose level.
 - 7.53 After enrolling 6 subjects on a specific dose level, if DLT is observed in 1 or less subjects, then the combination dose will be considered safe for the expansion phase. If DLT is observed in at least 2 of 6 subjects, then the MTD will have been exceeded and defined as the previous dose unless only 3 subjects were treated at the lower dose level. In that case, 3 additional subjects will be treated at this lower dose level.
 - 7.55 If a subject fails to complete one cycle of treatment for reasons other than dose-limiting toxicity defined adverse events, the subject will be regarded as non-informative for estimating the MTD and an additional subject will be treated at the current dose level.
- 7.6 Dose escalation (inpatient) will not be allowed for a subject.
- 7.7a For this protocol, the subject must return to the consenting institution for evaluation at least once per cycle.
- 7.7b Local Medical Doctor (LMD)
When it has been determined that a patient's malignant disease is stable or objective tumor regression has been observed and the patient is tolerating therapy without excessive toxicity, after the first cycle of treatment, the standard of care drug AraC may be administered by the patient's Local Medical Doctor

(LMD). However, study drug AZD1775 can only be dispensed by an investigator or investigational site of the study. The registering physician retains responsibility for the patient.

In this case, a written statement outlining drug dosage, method of administration, follow-up tests required, and telephone number to call to discuss any questions with the responsible investigator must be sent with the patient to provide necessary information to the LMD, post cycle 1 of treatment therapy. The LMD will be required to supervise the administration of the study drugs as stipulated in the protocol and provide written documentation that the drug was administered.

8.0 Dosage Modification Based on Adverse Events - If multiple adverse events are seen, administer dose based on greatest reduction required for any single adverse event observed. Dose modifications apply to the treatment given in the preceding cycle and are based on adverse events observed since the prior dose. Dose modification recommendations listed below are general guidelines, and appropriate dose adjustments for patient safety should be done if needed per treating physician discretion.

ALERT: ADR reporting may be required for some adverse events. See Section 10.0.

8.1 Dose Modification

Individual drugs can be dose reduced as per the table below depending on the adverse event attribution. The dose reductions outlined in table 8.11 should first generally apply to AraC. If, however, the AE is at least possibly related to AZD1775, then AZD1775 can be reduced first as indicated in Table 8.11. After cycle 2, these modifications should be regarded as guidelines to produce mild-to-moderate, but not debilitating, side effects. If multiple adverse events are seen, administer dose based on greatest reduction required for any single adverse event observed.

8.11 AZD1775 combined with AraC (Arms A and B)

Dose	AZD1775 [reduce AZD1775 first if at least possibly attributed to AZD1775]	Cytarabine (AraC)
0	300 mg PO once daily days 1-5 & 8-12	20 mg SC twice daily days 1-5 & 8-12
-1	250mg PO once daily days 1-5 & 8-12 ¹	20 mg SC twice daily days 1-5 & 8-12 ²
-2a	200 mg PO once daily days 1-5 & 8-12	20 mg SC twice daily days 1-5 & 8-12 ²
-2b	200 mg PO once daily days 1-5 & 8-12	10 mg SC twice daily days 1-5 & 8-12 ²

¹If toxicity is clearly attributable to AZD1775, AZD1775 will be reduced to 250mg PO daily (days 1-5, 8-12) with continued AraC 20 mg SC twice daily days 1-5, 8-12. ²AraC may be decreased to 10 mg SC twice daily at physicians discretion based on myelosuppression, tolerance and clinical benefit..

NOTE: intermediate dose levels may be explored based on PK, PD and clinical efficacy parameters and evaluation under future amendments based on PK, PD and safety assessments.

8.12 AZD1775 single agent (Arm C)

Dose	AZD1775
0*	300 mg PO once daily days 1-5 & 8-12
-1	250 mg PO once daily days 1-5 & 8-12
-2	200 mg PO once daily days 1-5 & 8-12
-3	150mg PO once daily days 1-5 & 8-12

*Presumed starting dose of Expansion Portion.

Note: Further dose modifications such as intermittent dosing or prolonged longer dosing can be made under future amendments.

- 8.2 A new course of treatment may begin on the scheduled Day 1 of a new cycle if:
- AZD1775 or AraC related adverse event that may have occurred has resolved to \leq Grade 2 severity, except hematological adverse events for WBC, ANC, Platelets and Hemoglobin, or per table 8.32 guidelines.

If these conditions are not met on scheduled Day 1 of a new cycle, the subject will be evaluated as clinically indicated (i.e. weekly but at least every other week) and the new cycle of treatment will not be initiated until the adverse event has resolved as described above. **Treatment can be continued on the drug that is not associated with the adverse event at the start of the following cycle and the drug associated with the adverse event may be reintroduced when the adverse event resolves to \leq Grade 1 if the treating physician feels that the patient will derive benefit from continued AraC or AZD1775 alone.**

NOTE: If the patient experiences a significant adverse event requiring a dose reduction at the start of the next cycle, then the dose will remain lowered for the remainder of the study

8.3 Dose modification table for adverse events felt to be at least possibly related to AZD1775*** or AraC

Non-hematologic toxicity management guidelines

Substantial acute toxicities should be managed as medically indicated and with temporary suspension of investigational product, as appropriate. Dose reductions or holds and initiation of supportive care are allowed as clinically indicated by the treatment physician.

Dose reductions of AZD1775 should be considered if toxicity is considered to be at least possibly related to AZD1775, i.e. in monotherapy studies or in combination studies if relationship cannot be wholly attributed to the combination agent (each combination agent should be considered on an individual basis). Dose re-escalation is not permitted.

In general, if a patient experiences a G1/G2 non-hematological toxicity, no dose modification is required (except QTc prolongation, see Table 8.31). If a patient experiences a G3 or G4 non-hematological toxicity which is not attributable to the disease or disease related processes under investigation, dosing will be interrupted and/or the dose reduced and

supportive therapy administered as required. Any patient who develops a Grade 3 or 4 non-hematologic toxicity that does not resolve to \leq Grade 1 within 21 days should be removed from the study treatment unless approved by the Medical Monitor and Study Chair.

No more than two dose reductions will be allowed for any patient. Patients requiring further dose reduction due to toxicity must discontinue study treatment. Dose re-escalation is not allowed. If the patient has concurrent neutropenia and thrombocytopenia, please follow the most conservative guidance in the table below and discuss with Medical Monitor as needed.

If haematological parameters do not recover within 21 days, the patient should be removed from the study treatment.

Table 8.31

Electrocardiogram QT corrected interval prolonged	
QTc Value (triplicate)^a	AZD1775
QTc 450-480 ms (males) or 470-480 (females)	Hold. Once QTc interval has returned to pretreatment status and correction of possible electrolyte imbalance has been made, resume at next lower dose level.
QTc 481-500 ms	Hold. Seek cardiologist advice, patient may resume at next lower dose level if cardiologist agrees.
QTc \geq 501 ms	Discontinue treatment. Seek cardiologist advice
Shift from baseline of \geq 60ms	Discontinue treatment. Seek cardiologist advice

Table 8.32

→ → Use the NCI Common Terminology Criteria for Adverse Events (CTCAE) version 5.0* unless otherwise specified ← ←			
CTCAE System/Organ/Class (SOC)	ADVERSE EVENT	AGENT	ACTION**
BASED ON INTERVAL ADVERSE EVENT***			
Blood and Lymphatic System Disorders	Febrile neutropenia \geq Grade 3	AZD1775	May omit dose until fever has resolved or returned to baseline. Dose to be restarted at same dose level or treating physician may discuss possible dose reduction (per Table 8.12) with the Study Chair. If clinical benefit is derived, AZD1775 may be continued if the infection is managed and controlled with appropriate medical intervention (i.e. antibiotics) and the patient is felt to derive benefit from the treatment with AZD1775 (Rationale: AML, MDS and MF patients may have persistent and/ or prolonged neutropenia and will only recover if underlying disease is adequately treated].

→ → Use the NCI Common Terminology Criteria for Adverse Events (CTCAE) version 5.0* unless otherwise specified ← ←			
CTCAE System/Organ/Class (SOC)	ADVERSE EVENT	AGENT	ACTION**
Investigations	Neutrophil & Platelet count decrease ≥ grade 4 NOTE: only applicable for patients with absolute neutrophil count (ANC) of ≥ 1000mm ³ and platelet count ≥ 100,000/mm ³ at baseline (i.e. MDS or MF patients)	AZD1775	Omit dose until ANC and/or platelets have recovered to ≤ grade 2. If clinical benefit is derived, AZD1775 may be continued if not recovered to ≤ grade 2 after discussion of treating physician and study chair. For a second event reduce by 1 dose level (Table 8.12) For a third event discontinue from treatment. [If clinical benefit is derived, AZD1775 may be continued per physician assessment and after discussion with Study Chair and Medical Monitor (NYU DSMC)]
Investigations	Creatinine increased Grade 2	AZD1775	Omit dose until resolved to ≤ grade 1, then: 
 • If resolved in ≤ 7 days, then maintain dose level • If resolved in > 7 days, then decrease by 1 dose level (Table 8.12) [If clinical benefit is derived, AZD1775 may be continued if the renal function is elevated but stable]
		AraC	Continue treatment at current dose level
	Creatinine increased Grade 3 and 4	AZD1775	Omit dose until resolved to ≤ grade 1, then decrease dose by 1 dose level
		AraC	Omit dose until resolved to ≤ grade 1, then decrease dose by 1 dose level
Investigations	Blood bilirubin increased ≥ Grade 3	AZD1775	Omit dose until resolved to ≤ grade 1, then: 
 • If resolved in ≤ 7 days, then maintain dose level • If resolved in > 7 days, then decrease by 1 dose level
		AraC	Continue treatment at next lower dose level
	Blood bilirubin increased Grade 4	AZD1775	Omit dose until resolved to ≤ grade 1, then decrease dose by 1 dose level

→ → Use the NCI Common Terminology Criteria for Adverse Events (CTCAE) version 5.0* unless otherwise specified ← ←			
CTCAE System/Organ/Class (SOC)	ADVERSE EVENT	AGENT	ACTION**
		AraC	Continue treatment at Dose level -1once resolved to ≤ Grade 1
	Alanine aminotransferase (ALT) increased and/or Aspartate aminotransferase (AST) increased Grade 3	AZD1775	Omit dose until resolved to ≤ grade 1 or baseline then: 
 • If resolved in ≤ 7 days, then maintain dose level • If resolved in > 7 days, then decrease dose by 1 dose level
		AraC	Continue treatment at next lower dose level
	Alanine aminotransferase (ALT) increased and/or Aspartate aminotransferase (AST) increased Grade 4	AZD1775	Omit dose until resolved to ≤ grade 1 or baseline, then decrease dose by 1 dose level
		AraC	Continue treatment at dose reduced AraC of 10mg s.c. twice daily days 1-5 & 8-12
Cardiac Disorders	Cardiac disorders – Other ≥ Grade 4	AZD1775	Omit dose and discontinue patient from study
Other Non-Hematologic events	Grade 3	AZD1775	Omit drug and follow patient at least weekly or at least every other week until adverse event has resolved to grade ≤ 2, restart drug at next lower dose level. Contact protocol chair and a medical monitor if resumption of AZD1775 at previous dose may be clinically indicated
Other Non-Hematologic events	≥ Grade 4	AZD1775	Omit drug and follow patient at least weekly or at least every other week until adverse event has resolved to grade ≤ 2, restart drug at next lower dose level. For a repeated Grade 4 event discontinue patient from study
AT TIME OF RETREATMENT (at beginning of each next cycle)			
Non Hematologic	All Non-Hematologic Toxicities Grade ≥ 4 (With the exception of nausea, vomiting or diarrhea controlled with appropriate medications.)	AZD1775	Hold AZD1775 and AraC. Re-check patient weekly or at least every other week. When event returns to ≤ grade 2, resume AZD1775 and/ or AraC treatment at next lower dose level. For a repeated Grade 4 event present/ recurred at beginning of each next cycle patient will be discontinued from therapy.

* Located at http://ctep.cancer.gov/protocolDevelopment/electronic_applications.ctc.htm

** Use the following to describe actions in the Action column:

- Omit = Treatment is not given for the day that is omitted, but treatment may resume once the adverse

event has resolved as mandated in Table 8.2. For example, if treatment is omitted on Day 8, but the adverse event has resolved by Day 10, treatment may resume on Day 10 to complete the cycle. Missed doses will not be made up.

- Hold/Delay = Treatment can be made up as part of this cycle
- Discontinue = Treatment is totally stopped

***AraC can be continued each cycle regardless of dose hold or adjustments for AZD1775, if patient is presumed to derive clinical benefit from the intervention.

Patients whose treatment is interrupted or permanently discontinued due to an adverse event including abnormal laboratory values must be followed by their treating physician as clinically indicated.

The maximum time allowed for treatment interruption due to toxicity is 4 weeks from the intended dosing day for the combination arms (Arm A and B) and 3 weeks for the single agent AZD1775 arm (Arm C). If interruption is > 4 and 3 weeks for Arms A, B and C respectively, continuation of treatment may be allowed on a case by case basis (i.e. clinical benefit) as determined by the treating physician in discussions with the Medical Monitor (NYU DSMC) and the Stuyd Chair. However, any discontinued patient will continue to be followed for toxicity. Dose interruptions should be reported on the appropriate Dosage Administration CRF.

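### Section 8 gives conflicting instructions for the same toxicity on Grade 4 bilirubin, the time limit, blood-count recovery and recovery grade, and leaves the cap on reductions unclear in Arm C

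*Combined protocol and SAP*

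**What the plan says.** **Starting a cycle and reintroducing a drug (Section 8.2).** A new cycle may begin once a related event is no worse than "Grade 2 severity, except hematological adverse events for WBC, ANC, Platelets and Hemoglobin, or per table 8.32 guidelines". The next paragraph lets treatment go on with the drug not associated with the event, and says "the drug associated with the adverse event may be reintroduced when the adverse event resolves to" Grade 1 or less.

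**Time limits and cap (Section 8.3, text above Table 8.31).** A Grade 3 or 4 non-hematologic toxicity not at Grade 1 or less within 21 days means removal, unless the Medical Monitor and Study Chair approve. Blood counts not recovered within 21 days mean removal, with no exception stated. "No more than two dose reductions will be allowed for any patient"; a patient who needs more must stop.

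**Table 8.32.** For other non-hematologic events of Grade 3, and of Grade 4 or more, AZD1775 is omitted "until adverse event has resolved to grade ≤ 2, restart drug at next lower dose level". The retreatment row, for Grade 4 or more, reads "When event returns to ≤ grade 2, resume AZD1775 and/ or AraC treatment at next lower dose level". One bilirubin row covers Grade 3 and above; the next is headed "Blood bilirubin increased Grade 4". The neutrophil and platelet row lets AZD1775 continue without recovery to Grade 2 after discussion with the study chair.

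**Notes below Table 8.32.** "The maximum time allowed for treatment interruption due to toxicity is 4 weeks from the intended dosing day" for Arms A and B, and 3 weeks for Arm C. Longer holds are decided case by case by the treating physician with the Medical Monitor and Study Chair.

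**Table 8.12 (Arm C).** The levels run from 300 mg (the presumed expansion start) through 250 and 200 mg to level -3, "150mg PO once daily days 1-5 & 8-12".

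**The concern.** These rules decide whether a patient with serious toxicity is treated again or withdrawn. Where two explicit rules cover the same patient and give different actions, two investigators can both follow the protocol and act differently. That is first a matter of patient safety and consistent conduct.

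It can also affect exposure. Sections 16.22 and 16.23 count CR/CRi over all cycles of treatment, so how long a patient stays on drug may bear on the chance of a response. In Section 16.23 an arm passes at 3 of 20 responders, and the comparison of Arms B and C turns on a 10-point difference, which is 0.10 × 20 = 2 patients.

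**Working it through.** The plan states no figure to reproduce. The check sets the rules side by side, with simple counts.

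**1. Grade 4 bilirubin (Table 8.32).** Grade 4 is also Grade 3 or more, so both rows apply.

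| Drug | Row for Grade 3 and above | Row for Grade 4 |
|---|---|---|
| AZD1775, resolved to Grade 1 or less in 7 days or fewer | same dose | one level lower |
| AZD1775, resolved in more than 7 days | one level lower | one level lower |
| AraC | continue at next lower level | level -1, only once at Grade 1 or less |

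The rows disagree for AZD1775 when recovery is quick, and on the timing of AraC whenever the event is unresolved.

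**2. Time limit.** Arms A and B: 4 weeks = 28 days in the notes, against 21 days in Section 8.3; 28 − 21 = 7 days (days 22 to 28). Arm C: 3 weeks = 21 days in both places; 21 − 21 = 0.

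These gaps assume a common starting day. The notes count from the intended dosing day; Section 8.3 names no start. If its clock starts at onset, k days before the intended dosing day, its limit falls 21 − k days after that day. The gaps become 7 + k days in Arms A and B and k days in Arm C. As an illustration, take an event that starts on Day 12, the last dosing day, and is unresolved at the next cycle:
- Arms A and B (28-day cycle, next dose due on day 29): k = 29 − 12 = 17, so the limit is 21 − 17 = 4 days after the due date, against 28. The gap is 24 days.
- Arm C (21-day cycle, next dose due on day 22): k = 22 − 12 = 10, so the limit is 11 days after the due date, against 21. The gap is 10 days.

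**3. Blood counts.** Take a patient whose counts have not recovered after 21 days. Section 8.3 removes the patient. Section 8.2 does not let WBC, ANC, platelets or hemoglobin block a new cycle. Table 8.32 lets AZD1775 continue after discussion if clinical benefit is derived, although that row covers only patients with baseline ANC of at least 1000 and platelets of at least 100,000. The febrile neutropenia row adds that these patients may have prolonged neutropenia that recovers only if the disease is treated.

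**4. Recovery grade.** Take an other non-hematologic Grade 3 event that falls to Grade 2 on day 10 and is still Grade 2 on day 21. Table 8.32 restarts AZD1775 one level lower. Section 8.3 removes the patient unless approval is given.

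**5. Number of reductions, Arm C (lesser point).** From 300 mg: 250 (one), 200 (two), 150 (three), against a cap of two. From 250 mg: 200 (one), 150 (two), within the cap. Table 8.12 does not say that level -3 is only for patients who start lower.

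**The case against.** The strongest reply is that Section 8.0 calls these recommendations general guidelines subject to physician discretion, and that the removal rule for non-hematologic toxicity and the notes name the same two roles for exceptions. This stands in part: it limits how far an individual site could choose for itself on those two rules. It does not say which explicit rule prevails, and neither the 21-day blood-count rule nor the cap carries an exception of its own.

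Other points have weight:
- The bilirubin overlap is probably a stray symbol, since the parallel ALT/AST rows are headed Grade 3 and Grade 4. The text still overlaps. The instruction in Section 8.0 to apply the greatest reduction concerns several events, not one event in two rows.
- Section 8.3 times the resolution of toxicity and the notes time the interruption, so a hold of 22 to 28 days is not automatically a removal. That is why the start of each clock has to be stated.
- Item 4 could be read in sequence: restart at Grade 2, then removal if Grade 1 is not reached by day 21. But Section 8.3 also says that Grade 1 or 2 toxicity in general needs no dose modification, and nothing sets out that sequence.

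A reader might also infer more than the text supports:
- **Section 8.2 contradicts itself on Grade 2 and Grade 1.** The Grade 1 sentence can be read as applying only when the other drug continues alone.
- **Grade 3 on Day 1 is a hold in Section 8.2 but not in Table 8.32.** The table's Grade 3 rows for creatinine, bilirubin, ALT/AST and other events omit AZD1775, and Section 8.2 itself refers to the table.
- **Table 8.32 always resumes at Grade 2.** Creatinine, bilirubin and ALT/AST require Grade 1 or less (or baseline, for ALT/AST). Thresholds that differ by organ are not a contradiction.
- **Table 8.12 permits three reductions.** It lists levels only, and Section 7.31 allows an MTD below 300 mg.

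**Conclusion.** The point holds for four conflicts (Grade 4 bilirubin, time limit, blood-count recovery, recovery grade) and one lesser ambiguity (the reduction cap against Table 8.12). In each of the four, the current text gives different actions for the same patient. The time-limit conflict is 7 days in Arms A and B and none in Arm C if the clocks start together; both gaps widen if the 21-day clock starts at onset. The cap matters only for Arm C patients who start at 300 mg.

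A reader might infer that these conflicts bias the CR/CRi rate or the choice between Arms B and C. The documents do not support that. They give no frequency of such holds or reductions and no link from them to response, so no effect can be computed. Stopping for toxicity does not by itself take a patient out of the evaluable denominator in Sections 16.22 and 16.23. The case rests on patient safety and uniform conduct, which is enough to warrant correction.

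**What to change.** Reconcile Sections 8.2 and 8.3, Table 8.12, Table 8.32 and its notes so that each combination of toxicity, grade and arm leads to one action:
- make the two bilirubin rows mutually exclusive for both drugs;
- state which time limit and which exception process govern each arm and toxicity type, and the day on which each clock starts;
- say how the 21-day blood-count rule relates to the exemption in Section 8.2 and to continuation under Table 8.32, and what counts as recovery;
- align the restart grade for other non-hematologic events with the removal rule, or state the order in which they apply;
- say how the cap of two reductions applies to Table 8.12 by starting dose.

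Which rule is right is a clinical decision for the sponsor. Organ-specific thresholds need not be made uniform. The cost is amendment wording; sample size and analysis are unchanged.

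### Table 8.32 lowers AraC by reference to dose levels that do not consistently define a required AraC reduction in Table 8.11 or Table 7.21

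*Combined protocol and SAP*

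**What the plan says.** Table 8.32 gives AraC six step-down instructions for Arms A and B:

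- Creatinine Grade 3 and 4: "Omit dose until resolved to ≤ grade 1, then decrease dose by 1 dose level".
- Bilirubin Grade 3 or higher: "Continue treatment at next lower dose level".
- Bilirubin Grade 4: "Continue treatment at Dose level -1once resolved to ≤ Grade 1".
- ALT/AST Grade 3: the same wording as for bilirubin Grade 3 or higher.
- ALT/AST Grade 4: "Continue treatment at dose reduced AraC of 10mg s.c. twice daily days 1-5 & 8-12".
- The retreatment row for Grade 4 or higher non-hematologic toxicity: both drugs are held, then one or both resume one level down.

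The levels for the combination are in Table 8.11. At levels 0, -1 and -2a the AraC entry is "20 mg SC twice daily days 1-5 & 8-12"; at -2b it is "10 mg SC twice daily days 1-5 & 8-12". Footnote 2, attached to the AraC cells of -1, -2a and -2b but not of level 0, lets the physician lower AraC to 10 mg twice daily. Table 7.21, the run-in table, shows 20 mg twice daily at every level. Table 8.12, to which several AZD1775 rows refer, has no AraC column.

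Section 8.1 sets the order of reduction: "The dose reductions outlined in table 8.11 should first generally apply to AraC". It adds that AZD1775 can go first if the event is at least possibly related to it. The text under Section 8.3 sets a ceiling: "No more than two dose reductions will be allowed for any patient".

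**The concern.** Five of the six AraC instructions depend on a level label, and the label does not settle the AraC dose. After the same Grade 3-4 hepatic or renal event, one physician can read the listed dose at the next level and leave AraC where it was. Another can use footnote 2 and halve it. Both are following the tables.

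These instructions apply after severe organ toxicity, so the first stake is patient safety. The second is interpretation: AraC exposure after toxicity in Arms A and B would partly reflect how the tables were read, and that exposure lies behind both the CR/CRi rate and the toxicity rate.

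**Working it through.** The plan gives no figure to reproduce. The check looks up each AraC instruction in the level tables.

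**AraC per cycle.** Dosing days are 1-5 and 8-12, which is 10 days, twice daily.

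- Listed dose: 20 mg × 2 × 10 = 400 mg.
- Reduced dose: 10 mg × 2 × 10 = 200 mg.

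| Level | AZD1775 once daily | AraC twice daily | AraC per cycle | Footnote 2 on AraC cell |
|---|---|---|---|---|
| 8.11, 0 | 300 mg | 20 mg | 400 mg | no |
| 8.11, -1 | 250 mg | 20 mg | 400 mg | yes |
| 8.11, -2a | 200 mg | 20 mg | 400 mg | yes |
| 8.11, -2b | 200 mg | 10 mg | 200 mg | yes |
| 7.21, 2 / 1 / 0 / -1 | 300 / 250 / 200 / 150 mg | 20 mg | 400 mg | not applicable |

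**Effect of one step on the listed AraC dose in Table 8.11.**

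- 0 to -1: 400 to 400 mg, no change.
- -1 to -2a: 400 to 400 mg, no change.
- -1 to -2b: 400 to 200 mg, a 50% fall. The table does not say whether -2a or -2b follows -1.
- -2a to -2b: 400 to 200 mg, a 50% fall.
- 0 to -1 with footnote 2 used: 400 to 200 mg, a 50% fall that is optional.

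**Starting level.** Table 7.22 sets the expansion AZD1775 dose at the MTD, not at a fixed 300 mg. Assume that a patient enters Table 8.11 at the row matching the dose received. An MTD of 300 mg enters at level 0, 250 mg at -1 and 200 mg at -2a. An MTD of 150 mg has no row.

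**Row by row.**

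1. *Creatinine Grade 3-4, bilirubin Grade 3 or higher, ALT/AST Grade 3, retreatment.* One level down leaves listed AraC unchanged from level 0. From -1 the result depends on which of -2a and -2b is taken. From -2a it does lower AraC.
2. *Bilirubin Grade 4.* The reference is to a fixed level. Level -1 lists 20 mg in Table 8.11 and in Table 7.21, although the AZD1775 dose under that label differs (250 and 150 mg). For a patient at 0, -1 or -2a, listed AraC does not change.
3. *ALT/AST Grade 4.* The row states the AraC dose and needs no lookup.

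**Combination missing from the ladder.** When Grade 3 bilirubin or ALT/AST resolves within 7 days, Table 8.32 keeps AZD1775 at its level and lowers AraC. From level 0 that means 300 mg of AZD1775 with less AraC. No row of Table 8.11 has this pairing, and footnote 2 is not attached to level 0. The listed step from level 0 does the opposite: AZD1775 falls to 250 mg and AraC stays at 20 mg.

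**Overlapping rows.** A Grade 4 bilirubin satisfies both bilirubin rows. One continues AraC a level down with no waiting condition. The other names level -1 and waits for recovery to Grade 1 or less.

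**Order of reduction.** Section 8.1 puts AraC first in general. The first step of Table 8.11 lowers only AZD1775.

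**Ceiling.** A patient who moves from 0 to -1 to -2a has used both permitted reductions, with AraC still listed at 20 mg.

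**The case against.** The strongest reply is that the plan leaves room to reduce AraC and says so. Footnote 2 first applies at level -1, so moving there is what makes 10 mg available, and tolerance, one of its stated grounds, can cover hepatic or renal toxicity. Section 8.0 calls the modifications general guidelines subject to physician discretion, and Section 8.3 allows reductions and holds as clinically indicated. Table 8.11 can also be read as the path for events attributed to AZD1775, with footnote 2 serving the rest. A patient whose MTD is 200 mg steps from -2a to a row where AraC does fall.

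All of this stands, and it rules out a stronger reading. A reader might infer that the ordered reduction is no reduction at all, or that sites are bound to give full-dose AraC after severe toxicity. The documents do not support that: a reduction is available at -1 and -2a, it is listed at -2b, and the Grade 4 ALT/AST row states one. Nor do they support the inference that sites would record a completed reduction while AraC was unchanged. The text after Table 8.32 asks only for dose interruptions to be reported on the dosing form.

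The reply does not remove the contradiction. Permission to reduce does not define what a row phrased as an instruction requires. Nor does discretion supply the missing pairing at level 0, choose between the two bilirubin rows, or decide whether -2a or -2b follows -1.

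**Conclusion.** The AraC level references in Table 8.32 do not consistently map to a required or defined AraC reduction. Five of the six AraC step-down instructions are affected; the Grade 4 ALT/AST row is not. From level 0, or from -1 to -2a, the listed dose stays at 400 mg per cycle, against 200 mg if footnote 2 is used. That is a twofold difference after the same event. From -2a the next row lowers AraC.

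This rests on Table 8.11 being the ladder that the AraC rows mean, and on patients entering it at the row matching their dose. The Grade 4 bilirubin result needs neither choice between tables nor a rule about -2a and -2b, because level -1 lists 20 mg of AraC in both tables.

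The documents give no rate for these events in Arms A and B, so the effect on average AraC exposure, CR/CRi or toxicity cannot be sized. Divergence between sites is a foreseeable risk, not an observed one.

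**What to change.** Reconcile Tables 7.21, 8.11 (with footnote 2) and 8.32 and Section 8.1 so that each AraC row points to one unambiguous AraC action. Two routes would do it: give AraC its own levels, separate from those of AZD1775, or state the AraC action in each row, as the Grade 4 ALT/AST row already does. The same edit should:

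- say which of -2a and -2b follows -1;
- make the two bilirubin rows mutually exclusive;
- provide for the case in which AZD1775 is maintained and AraC lowered;
- say which table the label -1 refers to;
- bring footnote 2 and the order of reduction in Section 8.1 into line with the result.

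The sponsor decides the doses. The cost is amendment wording in the tables and Section 8.1. It adds no patients or procedures and does not alter the sample size or the decision rules.
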